STUDY PROTOCOL

Nasal Intubation Using King Vision Video Laryngoscopy

[name]

(NCT03126344)

April 27, 2017

STUDY PROTOCOL

Title: A randomized controlled comparison of non-channeled King Vision, McGrath MAC video laryngoscope and Macintosh direct laryngoscope for nasotracheal intubation in patients with predicted difficult intubations.

Background: King Vision and McGrath MAC video laryngoscopes (VLs) are increasingly used. However, it remains unclear whether non-channeled King Vision or McGrath MAC VL, compared with conventional laryngoscope, provide shorter intubation time and a higher first success rate for NTI when used by experienced provider in management of predicted difficult intubation. It is also unclear whether non-channeled King Vision VL is superior to McGrath MAC VL when used for NTI.

Objective: To evaluate the performance of nasotracheal intubation in patients with predicted difficult intubations using non-channeled King Vision VL, McGrath MAC VL or Macintosh laryngoscope by experienced intubators.

Study Design: A single blind, three parallel arms, randomized controlled trial comparing NTIs using non-channeled King Vision VL, McGrath MAC VL and Macintosh DL in adults with predictors of difficult airways.

Subjects: Consecutive patients, between 18 and 60 years old with American Society of Anesthesiologists (ASA) classification of I or II, and requiring NTI for elective oral and maxillofacial surgery, were screened in the Preoperative Evaluation Unit of our institute.

Sample size: Based on the analysis of power analysis software, we take the type I error α as 0.05, the expected effect is 0.8, and the ideal test efficacy level is 0.8, then the minimum sample size of each group is 26. In order to reduce the loss of follow-up error, add 20% on this basis, then each group needs about 30 cases.

Recruitment method: Inpatients

Inclusion criteria: EGRI score 1–7.

Exclusion criteria: EGRI score > 7, history of reflux or diagnosed oesophageal disease, severe obstructive sleep apnea (OSA) and morbid obesity (body mass index > 40 kg/m²)

Study Methods:

1. Determine the subjects: select the patients who need nasotracheal intubation for elective operation, and determine 90 subjects strictly according to the inclusion and exclusion criteria, 30 in each group.

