2. Group: Patients were randomly assigned to King Vision group, McGrath group or Macintosh group via a computer-generated randomization table: King Vision video laryngoscope group (group K, n = 30), McGrath MAC video laryngoscope group (group M1, n = 30) and Macintosh laryngoscope group (group M2, n = 30).

3. Anesthetic methods: the anesthetic methods of three groups were the same. Patients were asked which nostril was clearer. If both sides were equal and the surgeon had no objection, the right nostril was chosen.

No premedication was administered. Lactated Ringer's solution infusion was started intravenously to deal with the fluid loss from the overnight fast after entering the operating theatre. A standard preparation was then performed, including heart rate (HR), lead II ECG, SpO₂ (pulse oximetry), and end expiratory carbon dioxide. A Bispectral (BIS) index sensor was attached to the patient's forehead in conjunction with the BIS Monitor. Cannulation of right radial artery was performed under local anesthesia for invasive blood pressure monitoring.

All patients were preoxygenated by a facemask in the position of neutral. Prior to anesthesia induction, the nasal mucosa was well prepared with 1% tetracaine hydrochloride jelly for 2 min and five drops of ephedrine hydrochloride nitrofurazone (containing approximately 2 mg ephedrine) in all patients. Baseline hemodynamic data were recorded by an investigator after a stabilization period of 10 min.

The nasotracheal tube used was reinforced endotracheal tube (ETT, Safety-Flex with Murphy Eye, oral/nasal, Athlone, Ireland; ID 6.5mm in female and ID 7.0mm in male patients) and was well lubricated with 1 % tetracaine hydrochloride jelly. Dosing of induction medications was given at the discretion of the attending anesthesiologists. Induction agents included midazolam (0.02 mg/kg), propofol (1.5~2 mg/kg) and fentanyl (2 µg/kg). Upon loss of consciousness and jaw relaxation, manual ventilation was tested. If manual ventilation was available, cisatracurium besilate (0.15 mg/kg) was administered and post induction values were recorded 3 min after induction. Unsuccessful manual ventilation led to study exclusion.

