The anesthesiologist tried to intubate when the Train of Four (TOF) count reached zero and BIS value decreased to 50. NTI was performed in a standard manner. First, a preformed ETT was inserted into the nostril and advanced to the posterior nasopharyngeal wall. Second, a laryngoscope blade was introduced into the mouth to expose the glottis. If it's necessary, the BURP maneuver (backward, upward, right-sided pressure) on the thyroid cartilage was attempted to obtain good glottis visibility. And ultimately, the ETT was inserted into the trachea with the aid of Magill's forceps, head flexion, or cuff inflation if necessary.

4. Observation outcome:

(1) Primary outcome: the intubation time

(2) Secondary outcome measures included time to expose the glottis (laryngoscopy time) and the view of glottis opening valued by Cormack-Lehane grade. A Cormack-Lehane grade IV was defined as laryngoscopy failure. A blinded investigator also recorded the hemodynamic changes (MAP, HR) during the procedure of NTI. The maximum values of invasive MAP were recorded. After successful intubation, the subjective sensation of the intubator (ease of device insertion, quality of view on display and ease of tube advancement) was graded as excellent, good, fair and poor. Other intubation parameters included incidences of bleeding or dental injury, number of assist maneuvers (use of BURP maneuver, Magill's forceps, or cuff inflation). Twenty-four hours after the procedure, a nurse anesthetist blinded to group assignment recorded the severity of sore throat and hoarseness.

Statistical analysis

Our sample size estimation was based on previous studies (11,23), in which the standard

deviations (SD) of intubation time were estimated as 8 and 13.7 seconds. To detect a intergroup difference of 10 seconds in intubation time with α of 0.05 and β of 0.8, we estimated that 30 patients would be enough for each group. To compensate for patients dropping out during the study, additional patients (10%) were added. The final sample size of 33 patients was in each group.

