Mean (SD) or Median (IQR [range]) was used to describe the parametric data. The number (percentage) was used to describe nonparametric data. Statistical analyses were performed with Prism 5.0 for Windows (GraphPad Software, Inc., La Jolla, California, USA). Binary data for three groups were analyzed using chi-square test and each two groups were compared with chi-square segmentation method or Fisher's exact test as appropriate. One-way analysis of variance (ANOVA) with post-hoc Bonferroni's Multiple Comparison test was used to analyze parameter data for changes within groups. The Kruskal-Wallis ANOVA with post-hoc Dunn's test was used to analyze ordinal data. A p value less than 0.05 was considered as significant.

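### Dunn's joint ranking makes the King Vision versus McGrath test on ordinal secondary outcomes depend on the Macintosh arm, and costs power if Macintosh is clearly worse

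*Combined protocol and SAP*

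**What the plan says.** The Statistical analysis section assigns one method to all ordinal outcomes: "The Kruskal-Wallis ANOVA with post-hoc Dunn's test was used to analyze ordinal data". The significance rule is "A p value less than 0.05 was considered as significant". Neither the sidedness nor the per-pair level for Dunn's test is given, and no separate two-arm rank test is planned.

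The secondary outcomes under Observation outcome include several that are ordinal or look so:
- "the view of glottis opening valued by Cormack-Lehane grade";
- three intubator ratings, each of which "was graded as excellent, good, fair and poor";
- 24-hour throat symptoms, for which a blinded nurse anesthetist "recorded the severity of sore throat and hoarseness" (no scale stated).

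The Background sets out two questions. One compares each video device with the conventional laryngoscope. The other compares the video devices with each other: "It is also unclear whether non-channeled King Vision VL is superior to McGrath MAC VL when used for NTI".

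The primary outcome, intubation time, is continuous and is not affected by this point.

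**The concern.** In Dunn's test all three arms are ranked together, and each pair's mean-rank difference is divided by a standard error built from the joint rank variance. The p-value for King Vision versus McGrath therefore changes with the Macintosh grades, although no Macintosh patient bears on that comparison.

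If Macintosh is clearly worse, two things follow. The video arms are pushed together at one end of the ranking, which compresses the difference between them. The joint standard error also includes the spread created by Macintosh, so it is too large for this pair. Both make the test conservative. At stake is power for one of the trial's two stated questions, on the secondary outcomes where Macintosh does badly.

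**Working it through.** **The plan's own figure.** The only sample-size basis in the Statistical analysis section is intubation time: n = 2 × (1.960 + 0.842)² × 13.7² / 10² = 29.5, so 30 per group, and 30 × 1.10 = 33. This reproduces. No power is stated for any ordinal outcome, so there is no ordinal figure to reproduce.

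**Inputs.** Three equal arms. The documents give 30 per group under Study Methods but also "The final sample size of 33 patients was in each group" under Statistical analysis; both were run. Assumptions: two-sided tests, Dunn with Bonferroni over three pairs (0.05 / 3 = 0.0167, critical value 2.394), tie correction throughout, and all grade distributions.

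**Formulas.** With N = 3n and S² the tie-corrected variance of the joint ranks, Dunn's z = (difference in mean joint ranks) / √(S² × 2/n). The two-arm Mann-Whitney z has the same form but uses ranks and variance from the 2n patients in that pair.

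**Limiting case by hand (no ties, n = 30).** If every Macintosh patient ranks worse than every video patient, the video arms fill ranks 1 to 60 and their mean-rank difference is the same in both tests. Only the divisor differs: Dunn uses √(90 × 91/12) = 26.1, Mann-Whitney √(60 × 61/12) = 17.5. Dunn's z is therefore 17.5/26.1 = 0.67 of the Mann-Whitney z. Passing 2.394 on Dunn's scale needs about 3.58 on the two-arm scale, a p-value of about 0.0003 against a nominal 0.0167.

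**Simulation (40,000 trials per scenario, n = 30).** Percentages are grades I/II/III/IV. Scenario 1: King Vision 70/25/5/0, McGrath 40/45/15/0. Scenario 2: King Vision 80/20/0/0, McGrath 50/40/10/0. King Vision versus McGrath power:

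| Macintosh arm | Dunn, 0.0167 | Mann-Whitney, 0.0167 | Mann-Whitney, 0.05, gated by Kruskal-Wallis |
|---|---|---|---|
| Scenario 1, poor (15/40/35/10) | 36% | 50% | 67% |
| Scenario 2, poor (15/35/40/10) | 34% | 58% | 75% |
| Scenario 1, mildly worse than McGrath (30/45/20/5) | 44% | 50% | – |
| Scenario 1, same as McGrath | 48% | 50% | 60% |
| Scenario 1, same as King Vision | 52% | 50% | 61% |

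At 33 per arm the two poor-Macintosh rows become 40/55/71% and 40/64/79%.

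**Splitting the gain.** Scenario 1: 67 − 36 = 31 points, of which 50 − 36 = 14 come from dropping joint ranks and 67 − 50 = 17 from gating at 0.05 in place of Bonferroni. Scenario 2: 41 points, split 24 and 17.

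**Mechanism.** In scenario 1, moving Macintosh from same-as-McGrath to poor cuts the mean-rank difference from 14.2 to 13.1 (about 8%) and raises the joint-rank SD from 23.5 to 24.3 (about 3%). The standardised difference falls from 14.2/(23.5 × √(2/30)) = 2.34 to 13.1/(24.3 × √(2/30)) = 2.09.

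**Error rate.** With identical video arms and a poor Macintosh arm, Dunn rejects King Vision versus McGrath in about 0.03% to 0.9% of trials, against a nominal 1.67%. When both arms follow the scenario 1 King Vision distribution, its standard error is about 6.1 while the true SD of the mean-rank difference is about 4.9. The gated Mann-Whitney test rejects in 4.8-4.9% against its nominal 5%.

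**Wider range.** For a third assumed pair (70/25/5/0 and 35/50/15/0; 20,000 trials, n = 30), Mann-Whitney at 0.0167 has about 64% power whatever Macintosh does. Dunn runs from 14% (Macintosh in grades III-IV only) through 37% (5/25/50/20) and 62% (same as McGrath) to 73% (all grade II).

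**The case against.** The strongest reply is that Dunn's test is a recognised follow-up to Kruskal-Wallis, its error for this pair is at or below nominal, and every affected outcome is secondary and was not used to size the trial. All of that stands: no false claim results from the planned method.

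Four stronger readings are tempting, and the documents do not support them.

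- **That the plan will hide a King Vision versus McGrath difference.** No expected grades are given for any arm, and the Background treats the advantage of video devices as unsettled. The table shows almost no loss when Macintosh is close to a video arm, and Dunn can even do better.
- **That a larger variance is the whole cause.** Without ties the joint variance is fixed at N(N+1)/12, yet power still falls as Macintosh moves away. Compression of the rank difference and a standard error too large for this pair act together.
- **That the whole rise from 36% to 67% comes from dropping joint ranks.** More than half of it comes from the change of multiplicity procedure. Keeping Dunn's statistic but gating at 0.05 would already give 56-57% in the two poor-Macintosh scenarios.
- **That every ordinal outcome is affected.** The loss requires Macintosh to be clearly worse on the outcome in question. For sore throat and hoarseness the documents state neither a scale nor an expected direction.

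**Conclusion.** The point holds as a conditional loss of efficiency. If Macintosh is clearly worse on an ordinal outcome, joint ranking costs about 14 to 24 percentage points of King Vision versus McGrath power at the same per-pair level, under the two main assumed scenarios at 30 per arm. If Macintosh resembles either video arm, the cost is about nil. The result is similar at 33 per arm, though the two stated group sizes should be reconciled.

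The figures rest on assumed grade distributions, two-sided tests, Bonferroni over three pairs and tie correction. The documents give nothing that places the trial within this range. The planned analysis is valid and the primary outcome is unaffected. A change is still worthwhile because it is cheap, bears on a stated question, and did better than Dunn with Bonferroni for this pair in every power scenario compared, including those where Macintosh equals a video arm.

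**What to change.** In the Statistical analysis section, replace the Dunn step by the following: for each ordinal outcome, a Kruskal-Wallis test across the three arms at 0.05; if it is significant, a two-sided, tie-corrected Mann-Whitney test for each pair at 0.05, using only the patients in those two arms.

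With three arms this is a closed procedure. If any two pairwise nulls are true, all three arms are equal, and the Kruskal-Wallis gate controls that case at 5%. If only one pairwise null is true, a single 5% test is exposed. Family-wise error over the three pairs is thus held at 5% within each outcome; it does not cover multiplicity across outcomes.

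The cost is one sentence and no new data. The downside is that the three pairwise tests no longer share a common ranking. If the team prefers to keep Bonferroni, two-arm Mann-Whitney tests at 0.0167 still remove the dependence on the third arm, but forgo the part of the gain that comes from gating.

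### About 12 secondary outcomes share one p<0.05 rule with no testing order, across-outcome correction or exploratory label; with no device effect, the chance of a false-positive secondary is 46% if independent, lower if correlated

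*Combined protocol and SAP*

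**What the plan says.** Item 4 of Study Methods (Observation outcome) names one primary outcome: "Primary outcome: the intubation time". Part (2) of that item then lists the rest without ranking them:

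- "Secondary outcome measures included time to expose the glottis (laryngoscopy time) and the view of glottis opening valued by Cormack-Lehane grade" (two outcomes).
- A blinded investigator "recorded the hemodynamic changes (MAP, HR) during the procedure of NTI. The maximum values of invasive MAP were recorded" (two outcomes, or three if maximum MAP is separate).
- The intubator's ratings: "ease of device insertion, quality of view on display and ease of tube advancement) was graded as excellent, good, fair and poor" (three outcomes).
- "incidences of bleeding or dental injury, number of assist maneuvers (use of BURP maneuver, Magill's forceps, or cuff inflation" (three outcomes, or more if the maneuvers are tested singly).
- At 24 hours, "a nurse anesthetist blinded to group assignment recorded the severity of sore throat and hoarseness" (two outcomes).

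The Statistical analysis section sizes the trial on intubation time alone. It assigns tests by type of data, not by outcome: chi-square with pairwise follow-up for binary data, ANOVA with Bonferroni for parametric data, and Kruskal-Wallis with Dunn's test for ordinal data. It ends with a general threshold: "A p value less than 0.05 was considered as significant". Nothing there sets an order among the secondaries, divides alpha between outcomes, makes secondary testing depend on the primary result, or labels the secondaries exploratory.

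**The concern.** Bonferroni and Dunn, as planned, answer one question: given a single outcome, which device pairs differ? They do nothing about the number of outcomes examined. With around a dozen outcomes each judged at 5%, the chance that at least one crosses the line by luck is well above 5%.

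What is at stake is how a secondary result may be reported. The Objective is framed as overall performance of nasotracheal intubation. The Background asks whether one video laryngoscope is superior to the other without tying that question to one outcome. If intubation time shows nothing, a nominally significant difference in view, ease, haemodynamics or complications could be presented as a device difference, and the stated rule would not prevent it.

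**Working it through.** **1. The plan's own figure.** The documents state no family-wise error rate. The only related calculation is the sample size for intubation time: difference 10 s, SD 13.7 s (the larger of the two quoted), two-sided α 0.05, and the stated β of 0.8 read as power 0.8.

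n per group = 2 × (1.96 + 0.842)² × 13.7² / 10² ≈ 29.5, rounded up to 30. Adding 10% gives 30 × 1.10 = 33.

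Both figures reproduce. The calculation concerns the primary outcome only and says nothing about the secondaries.

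**2. Number of secondary outcomes, k.** From part (2) of Observation outcome: laryngoscopy time, Cormack-Lehane grade, MAP, HR, three intubator ratings, bleeding, dental injury, number of assist maneuvers, sore throat, hoarseness. This gives 2 + 2 + 3 + 3 + 2 = 12.

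- Leaving out dental injury, as probably too rare to reject often: 11.
- Replacing the maneuver count with three separate maneuvers: 14.
- Keeping the count, adding the three maneuvers and adding maximum MAP: 12 + 3 + 1 = 16.

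**3. Independent outcomes.** With no device effect and a valid 5% three-arm test on each outcome, P(at least one p<0.05) = 1 − 0.95^k. For k = 12 this is 1 − 0.5404 = 0.4596, or 46%. The expected number of false positives is 12 × 0.05 = 0.6, whatever the correlation.

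**4. Correlated outcomes.** The documents give no correlations, so a common value from 0 to 0.8 is assumed. The first column is the closed form; the others are simulated null trials.

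| k | 0 | 0.3 | 0.5 | 0.8 |
|---|---|---|---|---|
| 11 | 43.1% | 37.6% | 31.0% | 18.7% |
| 12 | 46.0% | 40.3% | 33.2% | 19.4% |
| 14 | 51.2% | 44.0% | 36.2% | 20.5% |
| 16 | 56.0% | 48.2% | 38.6% | 21.4% |

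The rows for 11, 12 and 14 use one-way F tests with 30 per arm and 20,000 trials per setting. The row for 16 uses the large-sample chi-square form (2 df, 40,000 trials), which for k = 12 gives 40.0%, 32.1% and 19.4%. Using 33 per arm instead of 30 makes no material difference (45.7%, 40.7%, 32.9%, 19.7% for k = 12).

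**5. Data types closer to the plan's.** Most of the outcomes are ordinal or binary. A simulation with three continuous outcomes (ANOVA), seven ordinal (Kruskal-Wallis) and two binary (chi-square, one with an assumed 2% event rate), 30 per arm, gave 45%, 41%, 35% and 30% at latent correlations of 0, 0.3, 0.5 and 0.7. The rare binary outcome rejected only about 2% of the time. The normal-outcome model therefore does not exaggerate the problem.

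**6. What a correction would do.** Testing each of 12 outcomes at 0.05/12 = 0.0042 gives 1 − (1 − 0.0042)^12 ≈ 0.049 under independence, and about 0.041 at correlation 0.5.

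**The case against.** The strongest reply is that the plan does rank its outcomes. It names one primary, calls the rest secondary, and ties the sample size to the primary alone. By common convention, that makes the secondaries supportive. A reader might infer from the single threshold that there is no hierarchy at all, or that a secondary finding has the same standing as the primary. The documents do not support either inference: the threshold sentence is general, and nowhere do they say that a secondary result establishes superiority or can stand in for a null primary. What is missing is narrower: an order among the secondaries, a correction across them, or a statement that they are exploratory.

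A reader might also quote one figure, such as a one-in-three chance of a false secondary finding. That figure needs 12 outcomes with a common correlation near 0.5, which appears nowhere in the documents. The structure matters too: correlation of 0.5 only within four related blocks, and zero between them, gives 41%. Nor do these figures describe a trial whose primary result is non-significant. Conditioning on that gives about 30% at correlation 0.5 and 16% at 0.8.

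The family itself is a judgement. The plan does not map outcomes to tests, and bleeding, dental injury, sore throat and hoarseness could be set apart as complications. The remaining eight outcomes give 1 − 0.95^8 = 34% if independent, about 26% at 0.5 and 16% at 0.8. These points limit the precision of the figure. They do not bring it near 5%.

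**Conclusion.** The concern holds as a limited one. Under the stated rule, with no device effect and a valid 5% three-arm test on each of 12 secondaries, the chance of at least one nominally significant secondary result is 46% under independence. It falls as positive correlation rises, to 19% at 0.8, which is still nearly four times 5%. The range, not any one value in it, is the finding. It rests on the count of 12, on the assumed correlations, and on every within-outcome test holding its level. The last is a simplification, since the pairwise binary comparisons have no stated adjusted level.

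The error rate for intubation time is untouched, and no calculation in the plan is shown to be wrong. This is an inexpensive improvement to what the trial may conclude from its secondary outcomes.

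**What to change.** Replace the closing sentence of the Statistical analysis section with wording to this effect: the p<0.05 criterion, after correction for the three device pairs, applies to intubation time only; all other outcomes are exploratory, and their p values are nominal and do not by themselves support a claim that one device is superior.

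If the sponsor wants a confirmatory secondary claim, one or two outcomes could be named in advance (for example laryngoscopy time, then Cormack-Lehane grade) and tested in that order only if intubation time is significant, with the rest left exploratory. Such an order carries weight only if it is fixed before the data are seen.

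The change needs one or two sentences and no extra patients or data. The loss is that an isolated secondary p value below 0.05 can no longer be presented as an established device difference.
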